11.4 Data disclosure

11.5 Data safety and monitoring

11.6 Risk/benefit

11.6.1 Potential study risks

11.6.2 Potential study benefits

11.6.3 Risk/benefit assessment

## 1. Abstract

Patients with cancer often undergo costly therapy and acute care utilization that is discordant with their wishes, particularly at the end of life. Despite early palliative care consultations being an NCCN guideline-concordant practice in advanced cancer, palliative care referral rates for stage IV patients are low. In this project, we will evaluate a health system initiative that uses behavioral nudges to prompt palliative care referrals among outpatients with advanced cancer in terms of successful palliative care referrals and downstream quality of life outcomes. In partnership with the health system, this will be conducted as a 2-arm pragmatic cluster randomized trial.

## 2. Overall objectives

The primary objective of the study is to evaluate the impact of sending behavioral nudges to clinicians, as compared to usual practice, on completion of palliative care referrals among patients with advanced cancer. Our secondary objectives are to identify the impact of prompted palliative care referrals on quality of life, acute care utilization, and end-of-life utilization.

## 3. Aims

### *3.1 Primary outcome*

The primary outcome of the study is palliative care visits

### *3.2 Secondary outcomes*

- Change in quality of life between 0 and 9 weeks (as measured by the Functional Assessment of Cancer Therapy – General (FACT-G) among patients who receive palliative care compared to matched controls) (**Appendix A**)
- Quality of life at 9 weeks (as measured by the Functional Assessment of Cancer Therapy – General (FACT-G) among patients who receive palliative care compared to matched controls)

### *3.3 Exploratory outcomes*

- Unplanned 30-day emergency room and hospitalization rates (among all patients)
- Metrics of aggressive end-of-life care (systemic therapy within 14 days before death, no hospice enrollment prior to death; hospice enrollment <3 days before death) among decedents
- Documented advance care planning or serious illness conversations in the outpatient medical record
- Hospice referral and enrollment among all patients
- Overall survival, defined as date from enrollment to death

## 4. Background

Patients with advanced cancer have poor quality of life and life expectancy. Palliative care is a medical specialty focusing on providing relief from the symptoms and stress of serious illnesses such as cancer. While palliative care referrals often occur in the inpatient setting for acutely ill

individuals, early outpatient specialty palliative care concurrent with cancer-directed treatment improves quality of life and survival, is an evidence-based practice, and is endorsed by national guidelines. Palliative care can be provided in the ambulatory, telemedicine, or home-based settings. However, nearly half of patients with advanced cancer do not receive palliative care prior to dying. Lack of standardized referral criteria and screening methods for palliative care contributes to underutilization. There is a high need for strategies to increase use of palliative care in oncology.

Clinicians underutilize palliative care, initiating referrals a median of 2 months before death. This *status quo bias*, which predisposes clinicians to continue current practice even if not the optimal option, may lead to delayed or missed palliative care referrals. Additionally, *optimism bias*, the cognitive bias that causes clinicians to believe that their own patients are at lesser risk of negative outcomes, may cause clinicians to underestimate a patient's mortality risk or symptom burden, thus delaying palliative care referral. Finally, *overconfidence bias*, the propensity to overestimate one's desired behaviors when it is not objectively reasonable, may lead clinicians to incorrectly believe they are initiating more palliative care referrals than their peers.

Overcoming suboptimal clinician decision-making biases are key to increasing palliative care referrals. Principles from behavioral economics can inform "nudges" that change how clinicians receive information and make choices such as palliative care referral. Default, opt-out nudges that make the optimal choice the path of least resistance can mitigate clinicians' status quo bias. Reframing clinicians' prognoses by providing data-driven life expectancy assessments may combat optimism bias.

Early palliative care intervention can improve quality of life for patients with advanced cancer. Outpatient palliative care is available at 98% of NCI-designated cancer centers and 63% of non-NCI centers. Early outpatient palliative care concurrent with cancer-directed treatment improves quality of life, reduces symptom burden, and decreases rates of aggressive end of life care. Nevertheless, only a minority of patients who qualify for palliative care receive it.

## 5. Study design

### 5.1 Design

This is a 2-arm pragmatic randomized trial among approximately 250 outpatients with advanced cancer to assess response to behavioral nudges to refer to palliative care. The setting will be outpatient oncology at the Ann B. Barshinger Cancer Institute at Lancaster General Health. Eligible clinicians will be randomized in clusters by overlapping clinical team (pod) to receive default EPIC-based prompts for palliative care referral among advanced cancer patients (Arm 1) vs no intervention/usual practice (Arm 2). These nudges have been shown to positively influence clinician behavior and are often used to drive value-based oncology care; however, they have never been studied in the context of palliative care referral. The primary outcome is completion of a palliative care referral within 12 weeks of enrollment.

Following the intervention, brief REDCap questionnaires will be sent to all clinicians who participated in the trial to explore perceptions of the study intervention. This survey should take no longer than five minutes for clinicians to complete and will assess their feedback on the overall intervention in addition to specific components including automated identification of patients, receiving text and email notifications, and identifying the appropriate patients. The survey will also collect basic demographic information (age, gender, practice site, and comfort with SICs) (**Appendix 3**).

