#### *5.4 Accrual*

Patients will accrue to the trial according to their clinician pod in advance of a repeat patient visit. Any eligible patient cared for by an oncology outpatient clinician will be considered eligible.

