For patients whose clinician pods are randomized to the intervention arm, the care team pod will receive an EPIC in-basket message indicating that the patient is eligible for Palliative Care and that a default referral order has been pended for that patient. Clinicians will be given an opportunity to respond if they do not want their patient to be referred to palliative care. For clinicians who do not respond, after the allotted time, the Clinical Research Coordinator will reach out to the patient to introduce palliative care and ask if ABBCI staff can schedule an appointment. For non-English speaking patients, an interpreter will assist research staff. For clinicians who respond no, the pended order will be removed and no patient contact by the research team will occur.

For eligible patients whose clinician pods have been randomized to the control arm, no intervention will be provided. Clinicians will refer patients to palliative care based on their usual practice.

Among patients in the intervention arm for whom palliative care referral is placed, who accept for a scheduler to call them to make an appointment, a trained research coordinator will approach 40

patients as a convenience sample to administer a baseline FACT-G survey (**Appendix A**). 40 randomly selected patients, matched on categories including age category and type of cancer, will be selected from the pods not receiving the intervention. For patients that choose to enroll in the survey component, a baseline FACT-G survey will be administered prior to discharge in-person via paper or electronically. Surveys will be repeated at 3, 6, 9, and 18-week intervals by either telephone or in-person at an in-person visit. For patients that complete the 9-week survey or any survey prior, a \$50 gift card will be given at the 9-week time point. Patients who miss their visits with palliative care will be contacted by the coordinator to identify why (**Appendix F**) and reschedule the appointment.

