## 9. Analysis plan

We will use REDcap, a HIPAA-compliant and secure database tool, to track all components of the study. Descriptive statistics will be used to estimate the frequencies, means, and standard deviations of the study variables. Differences between study groups in baseline characteristics and clinical outcomes will be assessed with the use of two-sided Fisher's exact tests and chi-square tests for categorical variables and independent-samples Student's t-tests for continuous variables. The unit of analysis will be the patient.

The primary study endpoint is a binary patient-level variable indicating completion of a palliative care visit within 24 weeks of the clinician behavioral nudge. This analysis will be conducted as a time-to-event analysis among all eligible advanced cancer patients. Cox proportional hazard regression analyses, adjusted for baseline covariates, will be used to examine the effect of nudges on completion of palliative care consultation for advanced cancer patients. Competing risk caused by patients who die within 24 weeks will be considered as censored in the analysis. Covariates will include patient and cancer-related variables. Patients will be followed for 24 weeks or until death. Using a longitudinal multilevel mixed-effects model with clustering by discharging clinician (intraclass correlation coefficient 0.5 based on prior randomized trial); a two-sided type I error rate of 0.05; and a baseline palliative care visit rate of 45% (standard deviation 10%), we expect that a sample size of 250 patients will give us 80% power to detect a meaningful 34 percentage point response in palliative care visits, considering the presence of a competing risk of 6-month mortality at 20%.

One secondary outcome will be (1) change in quality of life between 0 and 9 weeks (as measured by the Functional Assessment of Cancer Therapy – General (FACT-G) among patients who receive palliative care compared to matched controls. Multivariate linear regression analyses, adjusted for baseline scores, will be used to examine the effect of palliative care on completion of palliative care consultation for advance cancer patients. For intention-to-treat analyses, we will use the conservative method of carrying the most recent quality-of-life values forward to account for all missing data, including data that are missing owing to death.

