#### *11.3 Subject privacy*

All efforts will be made by study staff to ensure subject privacy. Data will be evaluated in a de-identified manner whenever possible. We will require time and date of appointment and zip code data of trial participants to define our exposure period and link to area-level socioeconomic data from the American Community Survey.

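### The primary endpoint has two windows (12 and 24 weeks) and two starting points, and one of those starting points does not exist for control patients

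*Combined protocol and SAP*

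**What the plan says.** Four places define or describe the primary outcome:

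- Section 2 (Overall objectives): the effect of nudges "on completion of palliative care referrals among patients with advanced cancer". No window or starting point.
- Section 3.1 (Primary outcome): "The primary outcome of the study is palliative care visits". No window or starting point.
- Section 5.1 (Design): "The primary outcome is completion of a palliative care referral within 12 weeks of enrollment".
- Section 9 (Analysis plan): a binary patient-level variable for "completion of a palliative care visit within 24 weeks of the clinician behavioral nudge", analysed by Cox regression in all eligible patients. Patients who die within 24 weeks are censored, and follow-up runs to 24 weeks or death.

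On dates for control patients, Section 8.2 says that where the pod is "randomized to the control arm, no intervention will be provided". Section 5.4 says "Patients will accrue to the trial according to their clinician pod in advance of a repeat patient visit", which does not fix a date. Section 11.3 says the study needs "time and date of appointment and zip code data of trial participants to define our exposure period", without linking that period to the endpoint.

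The power statement in Section 9 assumes a 45% baseline visit rate, a 34-point effect, 250 patients, 80% power, an intraclass correlation of 0.5 and 20% six-month mortality. It names no window for the 45% or the 34 points.

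**The concern.** A primary endpoint needs one event, one window and one starting point that can be observed in the same way in every randomized patient. Here the window differs by a factor of two. The starting point is enrollment in one section and the nudge in another. The event also differs (referral or visit), though this is the softer conflict, since completing a referral can be read as attending the visit.

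The nudge is the intervention itself, so control patients have no nudge date. A Cox model needs time zero for everyone. Someone will have to choose a control date, and the plan does not say which.

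Three things are at stake. The Section 9 endpoint cannot be derived for controls by following the text. With two definitions open, the reported primary result could be picked after outcomes are known. And the power inputs generally cannot describe both windows, so it is unclear which endpoint the 250 patients were meant to serve.

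**Working it through.** **1. The two definitions side by side**

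| | Section 5.1 | Section 9 |
|---|---|---|
| Event | completed referral | completed visit |
| Window | 12 weeks | 24 weeks |
| Start | enrollment | clinician nudge |
| Start exists for controls? | yes, but the date is not defined | no |

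**2. The plan's own figure.** Comparing 45% with 79% (two-sided 0.05, 80% power) needs 31 per arm under individual randomization. A total of 250 then corresponds to a design effect of 250/62 = 4.03. With 1 + (m − 1) × 0.5 = 4.03, m = 7.1 patients per pod, or about 35 pods. The number of pods is not given, so the 80% can be neither confirmed nor refuted. Nothing in the calculation reveals the window.

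**3. What the window does to the rates (illustration).** Assumptions: 45% and 79% are 24-week rates, the 20% mortality applies at 24 weeks in both arms, and hazards are constant. With time in units of 24 weeks, the death hazard is b = −ln(0.8) = 0.2231. The cumulative incidence of a visit is

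F(t) = a/(a + b) × [1 − exp(−(a + b)t)].

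Solving F(1) = 0.45 and 0.79 gives a = 0.6848 and 1.9146. At 12 weeks (t = 0.5):

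- control: F = 0.2752
- intervention: F = 0.5881
- difference: 0.3128

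Front-loaded visits, using a Weibull visit hazard of shape 0.5 recalibrated to the same 24-week rates, give 0.3569 (control) and 0.6906 (intervention) at 12 weeks.

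| Visit pattern | Control, 12 wk | Intervention, 12 wk | Difference |
|---|---|---|---|
| Constant in both arms | 27.5% | 58.8% | 31 points |
| Front-loaded, intervention only | 27.5% | 69.1% | 42 points |
| Front-loaded in both arms | 35.7% | 69.1% | 33 points |

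The 12-week control rate is 9 to 17 points below 45%. Conversely, if 45% vs 79% are 12-week rates, constant hazards (a = 1.2802 and 3.4549) give 66.2% vs 91.6% at 24 weeks, a difference of 25 points.

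**4. Hazard ratio and information.** Under constant hazards the ratio is 1.9146/0.6848 = 2.80 for either window. The number of visits changes: with 125 per arm, 125 × (0.45 + 0.79) = 155 at 24 weeks and 125 × (0.2752 + 0.5881) = 108 at 12 weeks.

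**5. Shifting the control start by one week.** The sample timeline in Appendix 1 puts the nudge 7 days before the repeat visit. If control patients were timed from a date 7 days away from the matching one, constant hazards give:

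- 24-week window: F at 23, 24 and 25 weeks = 43.8%, 45.0%, 46.1%
- 12-week window: F at 11, 12 and 13 weeks = 25.7%, 27.5%, 29.3%

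The shift is therefore about 1 point and 2 points respectively.

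**The case against.** The strongest reply is that the document points to 24 weeks and that a common starting point is within reach. Section 9 uses 24 weeks for the endpoint, for censoring at death and for follow-up. Section 5.2 gives six months of follow-up, and the power sentence sits in the same paragraph and cites six-month mortality. Twelve weeks appears once, in a design summary. Coordinators identify patients with an upcoming repeat visit in both arms (Section 8.2), appointment dates are collected for all participants (Section 11.3), and survival is timed from enrollment. On this view the remedy is a wording correction.

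Much of this stands. The 24-week reading is better supported and is the one to adopt. The misalignment from a one-week slip is small, and smaller still if control visits are front-loaded (45.0% to 45.6% at 24 weeks). The hazard ratio itself need not move with the window. The Weibull shape is an assumption with no source in the plan, so the 42-point end of the range is a sensitivity case. With both arms front-loaded, the 12-week difference (33 points) is close to the planned 34.

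It does not remove the conflict. The 12-week sentence is an explicit statement of the primary outcome, and no text withdraws it. No section equates the nudge date with enrollment or assigns controls an equivalent date. The enrollment date itself is not pinned down for patients covered by the consent waiver, and the plan does not say that the identification date is recorded.

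**Conclusion.** The concern holds. The window and starting point contradict each other between Sections 5.1 and 9, and the Section 9 starting point is undefined in the control arm. That conclusion rests on the text alone.

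Its numerical size depends on assumptions, because the plan gives no window for its rates. If 45% vs 79% are 24-week figures with 20% mortality, the 12-week control rate is 9 to 17 points lower and the 12-week difference lies between 31 and 42 points, depending on how early visits occur. If they are 12-week figures, the 24-week difference is about 25 points under constant hazards. The likely bias from a misaligned control start is small. The point must be fixed because the primary result is not uniquely defined in advance and cannot be derived for half the design as written.

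**What to change.** 1. Put one definition in Sections 2, 3.1, 5.1 and 9: a completed palliative care visit within 24 weeks of the index date. This matches the stated follow-up and the visit-based power statement.
2. Define the index date by one rule for both arms, such as the date the coordinator identifies the patient as eligible, or a fixed interval before the identified repeat visit. Record it prospectively for control patients, without reference to later events.
3. State that the 45% and the 34 points refer to that 24-week window.
4. Keep referral and the 12-week result as secondary outcomes.
5. Optionally, report the 24-week difference in cumulative incidence, with death as a competing event, beside the hazard ratio. The power target is in percentage points under a mixed-effects model while the primary analysis is a Cox model, and this report would put the result on the scale of the target.

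The cost is wording in four sections, one date field for control patients and, if item 5 is taken up, one small extra analysis. The change should be made before outcome data are examined by arm.

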#### *5.2 Study duration*

The study is expected to begin in April 2022 and take 9 months (3 months for enrollment + 6 months total follow up) to complete. Our analysis will take place from December 2022 to March 2023.

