## 8. Study procedures

### 8.1 Consent

A waiver of informed consent is requested for the delivery of the palliative care nudge. This is a health system initiative that will be implemented and the study is to evaluate that initiative. Therefore, physicians and their patients will not be consented as this is the standard of practice per the health system initiative and national cancer guidelines. Without a waiver of the consent, the initiative would still be implemented by the health system, but the study would be infeasible. There are several additional reasons why we feel a waiver of consent should be granted. First, it is not feasible to consent every physician and as mentioned this initiative would occur with or without the study of it. Second, if members of the control group were consented, this alone could change their behavior. This could potentially disrupt the design of the study and making interpretation of the findings challenging. Third, physicians are not being forced to refer to palliative care for their patients. Instead, they are receiving behavioral nudges, including default EPIC-based nudges. This is no different than standard of care in which a physician would review the same information and decide to have a palliative care consultation. The initiative is simply a reminder for the physician and makes their standard of care process easier to conduct. Finally, as part of a previous quality improvement initiative, we interviewed nearly 40 clinicians after a trial testing a clinician nudge to perform serious illness conversations. We found no evidence of harm and found that serious illness conversations were considered standard of care for patients with cancer.

Patients who are selected for quality of life surveys will be consented over the phone for administration of FACT-G surveys at baseline (prior to hospital discharge) and at 3, 6, 9, and 18 weeks after enrollment. A copy of the informed consent form is available (**Appendix B**). Those who elect not to participate will be asked to grant permission (or not) for the study team to

collect limited data from them. An abbreviated Study Decline Consent form will be utilized for this purpose (**Appendix C**).

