### *8.2 Procedures*

Baseline data on oncologists and their patients at Lancaster General Health will be obtained from Penn Data Store and Clarity (Epic's data reporting database). Physician data includes demographic information (e.g. sex, type of medical degree, etc.) and may be also obtained from publicly available databases or websites online. Baseline data collected on patients will include age, gender, zip code of residence, type of cancer, Elixhauser comorbidity index, ECOG performance status, whether the patient is on active systemic therapy, and understanding of palliative care. This will be collected via the electronic health record and an in-person enrollment questionnaire (**Appendix D**) upon enrollment into the trial. Those who elect not to participate, but consent to limited data collection, will be asked to fill out a similar questionnaire including reason(s) for not wanting to participate in a de-identified manner (**Appendix E**).

Prior to the trial, staff will randomize each clinician pod in a 1:1 fashion to either intervention or usual care. The Principal Investigator ([name]) will be blinded to arm assignment. In both intervention and control arms, research coordinator staff will identify patients with advanced cancer who are actively cared for within the Ann B. Barshinger Cancer Institute system. They will then regularly review the electronic health record for eligible clinicians to identify patients with an upcoming repeat patient visit who are eligible for palliative care. Patients who are eligible will have a solid malignancy and at least one of the following five conditions: (1) Documented advanced (stage IV) solid malignancy; (2) Known central nervous system metastasis, (3) Eastern Cooperative Oncology Group performance status  $> 2$ , Karnofsky Performance Status  $< 50$ , (4) uncontrolled symptoms such as pain, escalating opioids, nausea/vomiting, distress, dyspnea, delirium, or (5) hospitalization relevant to cancer or treatment.

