## ***3. Sample Physician REDCap Questionnaire***

Thank you for participating in this questionnaire, which should take no more than 5 minutes. You have been asked to participate in this study because you were a part of an initiative starting May 2021. As you might recall, this intervention consisted of nudges for Palliative Care referral.

Please rate your agreement with the statements using the following:

- (1) Strongly disagree
- (2) Disagree
- (3) Neutral
- (4) Agree
- (5) Strongly agree

	1	2	3	4	5
Sentiment Overall					
I was satisfied with the overall experience of being involved in the study.					
Participating in the study helped me to increase Palliative Care referrals for patients.					
Identification of Patients					
It was helpful to receive names of patients who may be appropriate for Palliative Care referrals.					
The nudges accurately identified patients who were appropriate for Palliative Care referrals.					

The nudges motivated me to refer more patients to Palliative Care.						
Nudges						
I would have been more satisfied with different system of delivery than EPIC Inbox messages.						
The EPIC Inbox messages interrupted my clinical workflow in a negative way						
Experience						
The intervention led to more timely palliative care visits for my patients						

Please describe how the study could be improved.

[free text response]

Please tell us if you have any additional thoughts about your experience in this study.

[free text response]

Demographics					
What is your age?					
What is your gender?	Female	Male	Other		
Please select your comfort level with having a Serious Illness Conversation	Very uncomfortable	Uncomfortable	Neutral	Comfortable	Very comfortable
What do you consider to be optimal timing for Palliative Care?	At time of diagnosis	Within 3 months	At times of PC need	Following progression of cancer therapy	When out of treatment options

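### One nudge questionnaire goes to clinicians in both arms, and nothing holds it back until control patients have finished outcome follow-up

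*Combined protocol and SAP*

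**What the plan says.** On recipients and timing, Section 5.1 has one sentence: "Following the intervention, brief REDCap questionnaires will be sent to all clinicians who participated in the trial to explore perceptions of the study intervention". It gives no calendar date and no restriction by arm.

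On who the trial's clinicians are, the same section says "Eligible clinicians will be randomized in clusters by overlapping clinical team (pod) to receive default EPIC-based prompts", with usual practice as the comparator. Section 8.2 adds "Prior to the trial, staff will randomize each clinician pod in a 1:1 fashion to either intervention or usual care", and for the other arm "For eligible patients whose clinician pods have been randomized to the control arm, no intervention will be provided".

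On content, Appendix 3 holds a single sample form. Its introduction tells the recipient "you were a part of an initiative starting May 2021" and continues "As you might recall, this intervention consisted of nudges for Palliative Care referral". Section 5.2, by contrast, expects the study to start in April 2022.

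On the calendar, Section 5.2 says the study will "take 9 months (3 months for enrollment + 6 months total follow up) to complete". Appendix 1 places each nudge 7 days before the patient's repeat visit. Section 5.1 defines the primary outcome at 12 weeks from enrolment; Section 9 uses 24 weeks.

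On control behaviour, Section 8.1 argues for the consent waiver partly because "if members of the control group were consented, this alone could change their behavior".

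**The concern.** There are two separate problems.

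The first is fit. The survey is meant to learn how clinicians saw the intervention, but by its literal terms it also goes to clinicians who never had it. They are asked to rate messages and patient lists they did not receive, and the printed form offers no way to say so. If ratings are pooled, these answers blur the very information the survey is for.

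The second reaches the trial itself. The questionnaire names palliative care referral as the behaviour under study and asks when palliative care is best started. Section 8.1 requests a waiver of clinician consent, so for a control clinician this may be the first direct notice of the study. If it arrives while that clinician's patients can still have a primary-outcome event, it may prompt referrals in the comparison arm and shrink the measured difference.

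**Working it through.** **No plan figure to reproduce.** The documents give no sample size, response rate or analysis for the survey. Section 9's statement of 80% power with 250 patients is background only, and cannot be reproduced because the number and size of pods are not stated.

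**Step 1: which items need exposure.** Taking the rating items in Appendix 3 by block:

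| Block | Items | Presume nudges or their effect |
|---|---|---|
| Overall sentiment | satisfaction with being in the study; effect of taking part on own referrals | 1 of 2 |
| Identification | usefulness of names; accuracy; motivation to refer | 3 of 3 |
| Nudges | preference for another delivery route; workflow interruption | 2 of 2 |
| Experience | more timely visits | 1 of 1 |

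The total is 1 + 3 + 2 + 1 = 7 of 8. The scale runs from 1 to 5 with no not-applicable column, and no item records arm. Age, gender, comfort with serious illness conversations, optimal timing and the two free-text fields need no exposure.

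**Step 2: effect on pooled ratings.** If a fraction f of respondents are controls, a pooled mean is (1 − f) × (intervention mean) + f × (control mean), and the second term has no interpretation for the seven items. Allocation is 1:1 by pod, so f would be 0.5 only if the arms held equal numbers of clinicians and responded equally. Neither is stated, so f is unknown.

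**Step 3: how much follow-up could remain.** Assume uniform enrolment over 13 weeks (Section 5.2's 3 months), windows counted from enrolment, and a survey sent at week 13 when nudging ends. A patient enrolled at week t has max(0, W − (13 − t)) weeks left of a window of W weeks.

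- W = 24 (Section 9): mean elapsed time is 13/2 = 6.5 weeks, so the mean remaining is 24 − 6.5 = 17.5 weeks, and 17.5/24 = 73%. Every patient is still inside the window; the range is 24 − 13 = 11 to 24 weeks.
- W = 12 (Section 5.1): 12/13 = 92% of patients are still inside, with a mean of 6 weeks each. The overall mean is (12/13) × 6 = 5.5 weeks, and 5.5/12 = 46%.
- Sent after the last patient's window closes, at week 13 + 24 = 37 or 13 + 12 = 25: none remains under the corresponding definition.

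These are shares of calendar window. They ignore deaths and visits already completed, so true at-risk time is smaller.

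**Step 4: illustration of consequence (rise in controls assumed).** Take Section 9's 45% against 45 + 34 = 79%, and hold the effective size at 31 per arm, where the simple two-proportion formula gives 80%:

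power = Φ{[Δ√n − 1.96√(2p̄(1 − p̄))] / √(p₁(1 − p₁) + p₂(1 − p₂))}

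With p₁ = 0.45, this is Φ{(0.34 × 5.568 − 1.345)/0.643} = Φ(0.85) = 80%. Raising only the control rate to 47%, 50% or 55% gives about 75%, 67% or 52%. The documents give no basis for choosing among these rises. The intervention arm, which would receive the survey too, is held at 79%.

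**The case against.** The strongest reply is that early sending is nowhere planned. The end of the intervention is not equated with the end of enrolment, and Section 8.2 has coordinators rescheduling missed palliative care visits, so study activity continues after the last nudge. Section 5.1 refers to participation in the past tense, and the questionnaire looks back, asking for example whether visits became more timely. A survey after the trial is at least as natural a reading, and under it no contamination arises. This stands: a reader might infer that the survey is due at month 3, but the documents only leave that possible.

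A reader might also infer that Section 8.1 concedes that surveying controls alters referral. It does not; it speaks of a consent process. It supports the plausibility of a reaction to learning of the study and says nothing about its size. Section 11.2 adds that referral performance data already circulate to some providers, so the extra prompt could be small.

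A third tempting reading is that half of all answers are invalid and the survey cannot meet its aim. That goes too far. Intervention clinicians' answers remain usable, several items need no exposure, responses could be separated by arm if linked to pod, and the form is labelled a sample, so the built version may differ. The survey is also not a listed outcome and has no role in Section 9.

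What the reply does not remove is that the recipient rule covers both arms, the only form shown presumes exposure, and no sentence keeps the survey outside the outcome window.

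**Conclusion.** The point holds in two limited parts. First, as written, control clinicians receive a form on which about 7 of 8 rating items have no meaning for them; those answers are uninterpretable and would dilute pooled ratings to a degree that depends on an unstated control share. Second, the text permits the survey to reach control clinicians during endpoint follow-up. On the assumptions of uniform 13-week enrolment and sending at its end, about 73% of a 24-week window or 46% of a 12-week window would be left on average, before allowing for deaths and completed visits. A resulting rise in control referrals would pull the primary contrast toward no difference; whether one would occur, and how large it would be, is unknown.

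This should be corrected because the remedy is nearly free, but it is not a fatal flaw. The conflict between May 2021 and April 2022 is clerical on its own and implies nothing further about the trial's conduct.

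**What to change.** - In Section 5.1, state that no clinician survey goes out until the last enrolled patient in either arm has completed the primary outcome window. The 12-week and 24-week statements must be reconciled first, so that this date is defined.
- Send the nudge, identification and experience items only to intervention-pod clinicians. If controls are surveyed, give them a separate version with only the demographic and timing items, and without the introduction describing the nudge.
- Record arm for each response and report results by arm.
- Align the start date in Appendix 3 with the trial's actual start. In the same edit, reconcile the content: Section 5.1 says the survey covers text and email notifications and practice site, whereas the form asks only about Epic inbox messages and shows no practice-site item.

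The cost is a few sentences in Section 5.1, a short second form, and longer recall for intervention clinicians, whose last nudge could be up to one full outcome window before the survey, and earlier nudges longer still.
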